#### **ABBREVIATIONS**

ADCC Antibody-dependent cell-mediated cytotoxicity

GMT Geometric mean titers

HCP Healthcare Personnel

HA Hemagglutinin

HI Hemagglutination Inhibition

ILI Influenza-like illness

IIV Inactivated Influenza Vaccine

MDCK Madin-Darby Canine Kidney

GMR Geometric Mean fold rise

MN Microneutralization

NA Neuraminidase

NAI Neuraminidase antibody mediated inhibition

rHA Recombinant Hemagglutinins

RIV Recombinant Influenza Vaccine

SCR Seroconversion rate

SHIRI Study of Healthcare Personnel with Influenza and other Respiratory Viruses in Israel

#### 1. PROJECT SUMMARY

Healthcare personnel (HCP) are believed to be at increased risk of influenza virus infection due to a higher rate of exposure compared with the general population. Close contact with patients may further result in transmission to patients. Vaccination is the most effective method of preventing influenza, but there is limited information on the effectiveness of influenza vaccines among HCP. Some studies have demonstrated reduced influenza vaccine immunogenicity and effectiveness among persons with a history of frequent influenza vaccination, emphasizing the need to examine influenza vaccine effects among HCP who may be frequently vaccinated or demonstrate a high baseline immune response to influenza viruses.

The primary objective of the study is to compare humoral immune responses to a single dose of recombinant hemagglutinin quadrivalent influenza vaccines (RIV4) or to standard egg-

based unadjuvanted quadrivalent influenza vaccines (IIV4) among  $HCP \ge 18$  years old who were vaccinated in the 2018-19 season with IIV4. The trial will be conducted at two hospital sites in Israel during the upcoming influenza season (2019-20) among HCP who were enrolled in the Study of Healthcare Personnel with Influenza and other Respiratory Viruses in Israel (SHIRI).

The study design is a randomized, single-blind, trial. During the study, eligible HCP at each site who consent to participate will be randomized 1:1 to receive a single dose of RIV4 (Flublok™ Quadrivalent by Sanofi, Inc., 45µg of HA per strain) versus a single dose of IIV4 (VaxigripTetra™ by Sanofi, Inc., 15µg of HA per strain). Participants will be blinded to the vaccine that they receive; study staff will not be blinded. Eligible HCP who report already having been vaccinated with Vaxigrip at the time they are approached to join the study will be eligible to participate. All randomized participants will have blood collected just prior to vaccination; all participants, including those who were vaccinated with Vaxigrip outside of the study, will have blood collected , approximately 28 days after to evaluate humoral immune responses to vaccination. Relative efficacy of single doses of study vaccines will be assessed by comparing immunologic responses to vaccination among participants receiving RIV4 and those receiving IIV4. In addition, the effect of prior vaccination in potentially modifying antibody immune responses to vaccine will be evaluated.

#### 3. INTRODUCTION

# 3.1 Background Information

HCP are believed to be at increased risk of influenza virus infection due to a higher rate of exposure compared with the general population. Close contact with patients may further result in transmission to patients. Vaccination is the most effective method of preventing influenza, and HCP were identified by the World Health Organization as a priority population to target for influenza vaccination. However, there is limited information on the effectiveness of influenza vaccines among HCP. Reports of reduced influenza vaccine effectiveness among persons with a history of frequent influenza vaccination in some studies and seasons also make it especially important to examine influenza vaccine effects among HCP. Recent studies of influenza vaccine immunogenicity among HCP have demonstrated that repeated vaccination can blunt the antibody response to hemagglutinin (HA) and neuraminidase (NA).

Influenza vaccine efficacy varies annually depending on the match between vaccine strains and circulating strains, and by influenza virus type and subtype.  Reduced influenza vaccine effectiveness has been observed for A/H3N2 viruses over the past several influenza seasons in the United States,  and in Israel,  and has been associated with mutations that can occur during the production of inactivated influenza vaccines (IIV). Specifically, circulating influenza viruses are adapted for growth in embryonated chicken eggs, and then grown in large scale to produce the vaccine.  Both the adaptation process and serial passage of influenza viruses in chicken eggs can result in the development of mutations that have been associated with diminished vaccine effectiveness against both A/H3N2 and A/H1N1 viruses. 

New influenza vaccines manufactured without the use of eggs have been licensed in the United States, including a recombinant HA influenza vaccine (Flublok® by Sanofi Pasteur). Flublok® is formulated with purified influenza HA protein from cell-culture isolates of the vaccine reference virus. The influenza HA is grown using baculovirus vector technology that efficiently expresses the recombinant HA (rHA) proteins in large volumes in an insect cell line from the fall armyworm. The rHA is then purified from the cells and stored in phosphate-buffered saline (PBS). Since production of Flublok® does not use egg-adapted reference viruses, the rHA proteins may more closely match the vaccine reference virus for specific components in some seasons.

Flublok®, which contains more influenza antigen compared to most other vaccines licensed in the United States (45 µg vs. 15 µg of HA per strain in IIV), has been shown to be efficacious and immunogenic in a number of trials. In a phase III randomized placebo-controlled trial of trivalent Flublok® among healthy adults aged 18-49 years, Flublok® was 45% (95% CI 19-63%) efficacious against influenza infection during the 2007-2008 influenza season when the majority of circulating influenza A/H3N2 and B viruses were drifted from the vaccine strains. Flublok® was also found to be highly immunogenic for all three vaccine strains;  $\geq$ 96% of participants had an antibody titer of  $\geq$ 1:40 against each vaccine strain at 28 days post-vaccination. In a phase III randomized trial comparing quadrivalent Flublok® to quadrivalent Fluarix, an egg-based vaccine, among adults aged  $\geq$ 50 years, Flublok® was 30% (95%CI 10-47%) more efficacious against influenza infection during the 2014-2015 influenza season, when drifted A/H3N2 viruses predominated. Flublok® was found to be well tolerated, with equivalent reactogenicity compared to IIV. Flublok® was found to be well tolerated, with equivalent reactogenicity

Flublok® was licensed in the United States based on demonstrations of clinical efficacy and non-inferiority using immunogenicity outcomes according to the criteria of the Centers for Biologic Evaluation and Research. Sub-analyses in the clinical trials demonstrated a greater response to Flublok compared with IIV among previously vaccinated individuals. However, this same effect has not been studied among HCP, a population who are repeatedly vaccinated against influenza and frequently exposed to influenza viruses. It also remains unclear whether recombinant HA influenza vaccines that are free from mutations in the viral HA introduced during the egg adaptation and passage process of egg-based vaccine production are more effective against circulating influenza viruses compared to egg-based vaccines. Historically, the immunogenicity of influenza vaccines has been assessed by measuring antibody responses to egg-grown influenza viruses, which may be a suboptimal measure of efficacy if egg-grown viruses differ antigenically from circulating wild-type viruses. Studies evaluating Flublok have measured antibody responses to cell culture-grown viruses, but to date, there are few data directly comparing the immunogenicity of recombinant HA influenza vaccines to egg-based vaccines using the same immunogenicity outcome measures against the same antigenic targets.

This randomized, single-blind trial will assess humoral responses to recombinant HA quadrivalent influenza vaccine (RIV4, 45 $\mu$ g of HA per strain) compared with conventional eggbased quadrivalent standard dose (IIV4, 15 $\mu$ g of HA per strain) among HCP  $\geq$  18 years old using both cell-grown and egg-grown vaccine reference viruses as antigenic targets.

The primary study hypothesis is that a single dose of RIV4 may be more immunogenic than a single dose of egg-based standard-dose IIV4 to vaccine virus strain components among persons  $\geq 18$  years old.

#### 3.2 Justification

Influenza vaccines are the most effective method of influenza prevention. However, the efficacy of licensed influenza vaccines varies annually depending on the match between vaccine strains and circulating strains and varies by influenza virus type and subtype. Data from the last several influenza seasons showing lower vaccine effectiveness against influenza A/H3N2 viruses combined with studies documenting challenges with growing recently circulating influenza A/H3N2 viruses in embryonated chicken eggs for vaccine production have raised questions about the impact of egg adaptation and propagation of vaccine viruses on the effectiveness of

egg-based influenza vaccines. Furthermore, studies conducted among HCP repeatedly vaccinated for influenza have demonstrated a reduced antibody response to vaccination with IIVs. Influenza vaccines, including recombinant HA influenza vaccines, made by alternative methods of production that avoid the egg adaptation and/or egg propagation steps are now licensed in the United States. Studies are needed to compare the immunogenicity of conventional egg-based vaccines with vaccines manufactured using alternative methods of production using standard assays and endpoints. Data from such studies will inform whether a preferential recommendation for vaccines based on a specific method of production are warranted, particularly for HCP.

# 3.3 Expected benefits from the proposed study

Influenza results in substantial morbidity and mortality, and annual vaccination remains the most effective method to prevent influenza and its complications. Through this study, we will gain a better understanding of whether RIV4 (Flublok® Quadrivalent) offers greater protection to HCP than the conventional egg-based IIV4 (Vaxigrip® Quadrivalent) as measured primarily by humoral immune responses to MDCK cell-grown vaccine strains.

In the United States, both vaccines are licensed for use in adults aged  $\geq 18$  years based on phase III trials demonstrating efficacy in comparison to placebo or non-inferiority to conventional egg-based influenza vaccines. Therefore, study participants may directly benefit from receipt of study vaccine by receiving protection against circulating influenza viruses during the 2019-20 influenza season. In Israel, only IIV4 is licensed for use in adults aged  $\geq 18$ .

### 4. STUDY OBJECTIVES

## 4.1 Primary Objective

- Compare humoral immune responses to a single dose of RIV4 versus IIV4 at approximately 28 days after vaccination in the 2019-20 season among HCP ≥ 18 years old who were vaccinated in the 2018-19 season with IIV4 (defined as Group One) as measured by
  - hemagglutination inhibition (HI) titers for egg-grown influenza viruses A/H1N1,
     B/Yamagata, and B/Victoria, and egg-grown and cell-grown A/H3N2
  - o microneutralization (MN) titers for egg-grown and cell-grown A/H3N2 viruses

# 4.2 Secondary Objectives

- Compare humoral immune responses to a single dose of RIV4 versus IIV4 at 28 days post-vaccination in the 2019-20 season among HCP with a history of PCR-confirmed influenza infection during any of the three study years (2016-17 through 2018-19) compared to those without PCR-confirmed influenza infection (defined as Group Two);
- Compare humoral immune responses at 28 days post-vaccination as stated in the primary objective but with secondary indicators of humoral immune response using MN titers for other virus subtypes/lineages, as appropriate;
- Examine whether the number of prior influenza vaccinations during the preceding 10 years, as documented by medical records, modifies humoral immune responses after a single dose of RIV4 or IIV4 at approximately 28 days after receipt of the 2019-20 vaccines as measured by
  - HI titers for influenza A/H1N1, influenza B/Yamagata, and influenza B/Victoria strains and
  - o MN titers for influenza A/H3N2 viruses

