# 5. STUDY ENDPOINTS

# **5.1 Primary Endpoints**

The primary endpoints will be assessed by the following laboratory tests. The choice of laboratory assay may depend in part on how the 2019-2020 vaccine components and circulating strains affect which laboratory assay is most effective in assessing specific antigens.

- HI and/or MN responses to *egg*-grown vaccine reference viruses for all vaccine viruses for each study season at approximately 28 days, including the following endpoints
  - o Seroconversion rate (SCR) defined as the proportion of participants with paired samples that achieved ≥4-fold rises comparing post- versus pre-vaccination titers
  - Geometric mean titers (GMT) and the ratio of post-vaccination titers between the two vaccines (post-vaccination GMT ratio);
  - Geometric mean-fold rise (GMR) defined as the ratio of the post-vaccination titer
     value to the pre-vaccination value
  - o Elevated post-vaccination titers at thresholds greater than 1:40, 1:80, 1:160
- MN responses to the *cell*-grown influenza A/H3N2 (using MDCK-SIAT or other appropriate cell line) vaccine reference viruses at approximately 28 days postvaccination, including the following endpoints:
  - o SCR, post-vaccination GMT ratio, GMR, and elevated post-vaccination titers

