### Inclusion criteria:

- 1. Aged ≥18
- 2. Are currently a member of Clalit Health Services
- 3. Consent to randomized receipt of influenza vaccination with either RIV4 or IIV4, or, if already vaccinated in the current year outside of the study, consent to receive a post-vaccination blood draw
- 4. HCP Group One participation criteria:
  - Participated in the SHIRI study and received influenza vaccination during the
     2018-19 influenza season
- 5. HCP Group Two participation criteria:
  - Participated in any year of the SHIRI study and had PCR-confirmed influenza virus infection during any of the three study years;
- 6. HCP Group One Supplemental criteria:
  - Participated in any year of the SHIRI study, not vaccinated in 2018-2019, but vaccinated in at least one study year;
  - Participated in the SHIRI study during all three years, regardless of vaccination status

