#### 9. DATA ANALYSIS

# 9.1 Power and Sample Size Considerations

To guide enrollment goals, we estimated the sample size required to do a two-sided test with a significance level of 0.05 and a power of 80%. The Food and Drug Administration criteria for demonstrating non-inferiority between IIV and a new vaccine requires comparisons of both the GMR and the SCR. We based expected values for the SCRs and GMRs comparing RIV3 and IIV3 on previously published estimates from prior vaccine immunogenicity trials. We assume that the SCR for IIV4 is  $\geq$ 40% and  $\geq$ 55% for RIV4, based on a clinical trial among adults <65 years demonstrating the SCR for IIV4 to range from 35% to 60% and RIV4 to range from 54%

to 63% against influenza A subtypes (seroconversion rates reported against influenza B viruses reflected trivalent vaccine formulations and were not included).  $^{23,32}$  We intend to have the power to show a 30% relative increase in SCR in the RIV arm compared to the IIV arm. Using the same assumptions and sample size would also provide adequate statistical power to detect a difference in post-vaccination GMT of  $\geq$ 2 fold between study arms if post-vaccination GMT value is  $\geq$ 20 for IIV4 and  $\geq$ 40 for RIV4. **Table 2** provides estimated sample sizes required for varying SCR and differences in SCR between study arms.

Based on prior experience enrolling participants at the two study sites, we will assume that 5% of participants will drop out before study visit 2.

Table 2. Sample size calculations to detect specified differences in SCR between RIV4 and IIV4 at approximately 28 days post-influenza vaccination

SCR at 28 days post- vaccination in IIV arm	Relative increase (%) in SCR in RIV arm compared to IIV arm at 28 days post-vaccination	IV arm Total enrollment for both study arms	
30%	10%	7526	
30%	20%	1926	
30%	30%	874	
40%	10%	4778	
40%	20%	1208	
40%	30%	540	
50%	10%	3130	
50%	20%	776	
50%	30%	340	
60%	10%	2032	
60%	20%	488	
60%	30%	206	

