## Secondary Objectives

To compare immune responses among Group Two participants with a history of PCR-confirmed influenza infection a linear regression predicting log transformed titer will be created with independent variables for year of influenza infection, type of influenza virus detected, study arm, and potential confounders. We assume confounding will be eliminated by randomization and that models will not be adjusted unless differences in study arms are found during univariate analysis.

To assess prior vaccination status among Group One participants (number of influenza vaccinations received during the preceding 10 years) as an effect modifier of differences in GMTs, a linear regression predicting log transformed titer will be created with independent variables for vaccine history, study arm, and potential confounders, and an interaction term between study arm and vaccine history.

All primary analyses will be conducted as intention-to-treat. All tests will be 2-tailed with a level of significance of .05.

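### The model planned for the first secondary objective has no uninfected comparator and no infection-by-arm term, so as written it cannot show whether prior influenza changes the RIV4–IIV4 difference

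*Combined protocol and SAP*

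**What the plan says.** Section 4.2 defines the exposure as a "history of PCR-confirmed influenza infection during any of the three study years (2016-17 through 2018-19) compared to those without PCR-confirmed influenza infection" and attaches the label Group Two to this comparison. The Group Two entry criterion in section 6.3.1 covers the infected side only: participants who "had PCR-confirmed influenza virus infection during any of the three study years". Neither place names a type, subtype or lineage.

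The outcomes are specific to a virus. Section 5.1 takes responses to "vaccine reference viruses for all vaccine viruses for each study season", and section 4.1 lists A/H1N1, A/H3N2, B/Yamagata and B/Victoria.

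The analysis for this objective is in section 9.2 under Secondary Objectives. It opens "To compare immune responses among Group Two participants with a history of PCR-confirmed influenza infection" and specifies a linear regression on log titre with "independent variables for year of influenza infection, type of influenza virus detected, study arm, and potential confounders". No uninfected group is named and no interaction is listed. The next paragraph, on vaccination history, does specify "an interaction term between study arm and vaccine history".

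**The concern.** The objective and the model ask different questions. The objective sets the RIV4–IIV4 comparison in infected participants against the same comparison in uninfected participants. The model describes titres within the infected group alone, with one arm effect.

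Three gaps follow:

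- Without uninfected participants, no infected-versus-uninfected contrast can be estimated. Year of infection and type of virus have no value for someone never infected, so the model cannot be extended to them without a further coding rule.
- With arm and type as main effects only, the RIV4–IIV4 difference is forced to be equal whether or not the infecting virus matches the antigen being analysed.
- Type is not defined. Sections 3.1 and 3.2 mention type and subtype separately, and section 4.2 speaks of subtypes and lineages. Type may therefore mean only A versus B, which puts H1N1 with H3N2 and Yamagata with Victoria.

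At stake is whether the first secondary objective gets a prespecified answer. If the comparator, coding and interaction are settled after titres are seen, the result depends on choices made with the data in view.

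**Working it through.** **The plan's own figure.** Section 9.1 sizes the trial on seroconversion between arms: "We intend to have the power to show a 30% relative increase in SCR in the RIV arm compared to the IIV arm". For 40% versus 52%, two-sided 0.05 and 80% power:

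n per arm = [1.960·√(2·0.46·0.54) + 0.842·√(0.40·0.60 + 0.52·0.48)]² / 0.12² = 269.6, rounded up to 270, or 540 in total.

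This reproduces Table 2. It sizes the arm comparison; the documents give no sample size or power for the first secondary objective.

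**Objective against model.** For one antigen, write μ for mean log2 titre by arm (R, I) and infection history (1 = infected, 0 = not). The objective needs

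Δ = (μ_R1 − μ_I1) − (μ_R0 − μ_I0).

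The planned model, fitted in Group Two, is

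E[log2 titre] = α + year + type + θ·arm + confounders.

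It supplies θ, an estimate of μ_R1 − μ_I1 averaged over infecting viruses. The terms μ_R0 and μ_I0 are absent, so Δ is not estimable. Adding uninfected participants with a level for no infection would still leave a single θ for everyone, which sets Δ to zero by construction. Only an infection-by-arm term makes Δ a quantity the model can estimate.

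**Who is uninfected.** Section 6.3.1 defines Group One by SHIRI participation and 2018-19 vaccination, not by absence of infection. A Group One member may have had PCR-confirmed influenza. Enrolment group is therefore not a valid proxy for infection history.

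**Cell sizes and precision.** Targets of 110 and 440 (section 6.3.2) less 5% dropout (section 9.1) give 110 × 0.95 = 104.5, taken as 104, and 440 × 0.95 = 418. Assume for illustration that all 418 are uninfected. With 1:1 arms, the standard error of an infection-by-arm contrast is 2·SD·√(1/n + 1/418), where n is the number in the infected category. The matched share f and the SD are not in the documents; f of 25–75% and SD of 1.5–2.0 log2 are assumptions. The last column is the factor by which the fold estimate is multiplied and divided to give a 95% interval, 2^(1.96 × SE).

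| Contrast with none | n (per arm) | SE / SD | 95% factor, SD 1.5 to 2.0 |
|---|---|---|---|
| Any infection | 104 (52) | 0.219 | 1.56 to 1.81 |
| Matched, f = 75% | 78 (39) | 0.247 | 1.65 to 1.95 |
| Matched, f = 50% | 52 (26) | 0.294 | 1.82 to 2.22 |
| Matched, f = 25% | 26 (13) | 0.404 | 2.28 to 3.00 |

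**Should matched versus none replace any versus none?** Let unmatched infection carry a share h of the matched log2 effect. The pooled effect is then f + (1 − f)h of the matched one. At f = 25% the matched standard error is 0.404/0.219 = 1.84 times the pooled one. The ratio of pooled to matched signal-to-noise is 1.84 × (0.25 + 0.75h): 0.46 at h = 0 and 1.15 at h = 0.5, with break-even near h = 0.39. SD cancels. Which contrast is more sensitive therefore depends on f and h, and the documents give neither.

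**The case against.** The strongest reply is that section 9.2 already handles the infecting virus. It enters both type and year of infection, so an influenza B infection is not coded like an influenza A infection. That stands, and it limits the point. A reader of sections 4.2 and 6.3.1 might infer that the analysis pools all influenza into one exposure and so dilutes a strain-specific effect. The documents do not support that reading: within Group Two the type term separates infecting viruses for the level of titre, as far as type distinguishes them. It does not separate them for the arm effect, and it supplies no uninfected group.

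A reader might go further and claim a definite gain in power from coding infection as matched to the antigen. That claim needs unmatched infection to have no effect, together with a strain mix and an SD that the documents do not give. If unmatched infection carries half the effect, the any-infection contrast is the more sensitive one at 25% matched. No power gain should be claimed.

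It can also be said that the Group Two arm effect could be set beside the Group One result. That would be an informal comparison of two estimates, not a test of their difference, and Group One is not an uninfected group.

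Finally, section 6.7 promises linkage of all SHIRI data but does not say that positive PCR results were subtyped. That stands too. Matching may be possible only on type for some participants, which would again mix subtypes or lineages.

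**Conclusion.** The point holds as a gap between objective and model. The first secondary objective concerns how the RIV4–IIV4 difference varies with infection history. The model in section 9.2 has neither the uninfected participants nor the interaction needed to estimate that. This follows from the text alone and rests on no numerical assumption.

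The consequence is confined to one secondary objective. The data to answer it should exist, since uninfected SHIRI participants can enter through Group One and PCR history is to be linked; what is missing is the specification. Any bias or power loss from pooling infecting viruses cannot be sized from the documents. The precision figures above illustrate the cost of the fix and depend on the assumed matched share, SD and number uninfected.

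**What to change.** Rewrite the first paragraph under Secondary Objectives in section 9.2, and align section 4.2 with it:

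1. For each antigen, fit the log-titre regression in infected and uninfected participants together, classifying each by SHIRI PCR history and not by enrolment group.
2. Code infection history as same subtype or lineage as the antigen (same type where only A or B is known), other influenza only, or none. State that this replaces the undefined type variable, and that a participant with several infections counts as matched if any one matches.
3. Include the interaction of infection history with study arm. Keep the potential confounders, because infection history is not randomised.
4. Report any-versus-none, the objective as stated, together with matched-versus-none and other-versus-none. Do not substitute matched-versus-none for it.
5. Say how year of infection will be used, for example as a descriptive analysis among the infected.

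The cost is wording and recoding of data that the plan already intends to link, with no new participants, visits or samples. The downside is small matched cells: 104 × 0.25 = 26, about 13 per arm if a quarter are matched, with intervals on the log scale 1.84 times as wide as for any infection. The matched contrasts should be presented as estimates with intervals, and a wide interval should not be read as evidence of no difference.
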